9.12 Trial restrictions

Patients should avoid taking potassium supplements (including dietary substitutes such as Lo-Salt) or potassium sparing diuretics other than MRA unless required for the management of hypokalaemia.

Use of strong CYP 3A4 inhibitors and combined use of both an ACE inhibitors and ARB should be avoided. Most if not all patients will have renal dysfunction and therefore the use of non-steroidal anti-inflammatory drugs should be avoided where possible. Use of non-evidence based medicines and over-the-counter treatments including herbal and other dietary supplements are discouraged.

Patiromer should not be taken within three hours of other oral medications. Patiromer should be mixed with water or apple juice, as directed.

9.13 Assessment of compliance with treatment

Compliance will be estimated at each trial visit by research staff and participants, and documented in the eCRF. For those treated with both patiromer and MRA, research staff must assess compliance with both IMPs to ensure that both are taken as intended. For those receiving both patiromer and MRA, poor compliance (<80%) should be discussed with the participant, their safety evaluated and consideration given to withdrawing patiromer and reverting their management to standard care with

Version 5.0 22 July 2021 Page 51 of 82

MRA alone. Poor compliance with MRA should also be discussed with the participant and the benefits of MRA emphasised.

Patients must be withdrawn from treatment with IMP(s) if the investigator considers it unsafe for them to continue. Safety will be assessed by research nurses and/or investigators at each visit and after the occurrence of each SAE/SAR. Participants who have had an SAR (e.g. a hospital admission for the management of hyper- or hypo-kalaemia) should be reassessed for their ability to understand and comply with IMP dosing instructions.

- If the participant is, in the investigator's opinion, no longer able or willing to comply with treatment instructions, then they should stop one or both IMP and revert to standard-care, even if they have not experienced an SAE or SAR.
- Participants who are assigned to patiromer and who have or develop hyperkalaemia (serum potassium >5.0mmol/L), even if they have been withdrawn from spironolactone or eplerenone IMP, may continue on or restart patiromer.
- For participants with recurrent (two or more within a 6 month period) or life-threatening hyperkalaemia, investigators should reduce the dose of spironolactone or eplerenone to a maximum of 25mg/day or less (this includes a zero-dose), unless in the opinion of the investigator the benefit/risk ratio of receiving higher doses of spironolactone / eplerenone IMPs is still believed to be positive (e.g. the participant's heart failure has responded well to higher doses of spironolactone or eplerenone). Participants assigned to patiromer should have the doses adjusted to achieve a serum potassium between 4.1 to 4.9mmol/L (inclusive).

IMP may be re-initiated at any time if the investigator believes it is safe to do so and the participant is willing.

Compliance will be encouraged by patient information leaflets and education. However, even if a patient is withdrawn from IMP they should be followed according to the protocol. Patients who decline to attend trial visits will be unable to obtain trial IMP and therefore will revert to standard care. If the participant agrees, they will continue to be contacted by the investigator or followed through their medical record even if they decline to attend trial follow-up visits.

Version 5.0 22 July 2021 Page 52 of 82

10. SAFETY AND OUTCOME REPORTING

10.1 Definitions

Term	Definition
Adverse Event (AE)	Any untoward medical occurrence in a participant to whom a medicinal product has been administered, including occurrences which are not necessarily caused by or related to that product.
Adverse Reaction (AR)	An untoward and unintended response in a participant to an investigational medicinal product which is related to any dose administered to that participant. The phrase "response to an investigational medicinal product" means
	that a causal relationship between a trial medication and an AE is at least a reasonable possibility, i.e. the relationship cannot be ruled out.
	All cases judged by either the reporting medically qualified professional or the Sponsor as having a reasonable suspected causal relationship to the trial medication qualify as adverse reactions. It is important to note that this is entirely separate to the known side effects listed in the SmPC. It is specifically a temporal relationship between taking the drug, the half-life, and the time of the event or any valid alternative aetiology that would explain the event.
Serious Adverse Event (SAE)	A serious adverse event is any untoward medical occurrence that: results in death is life-threatening requires inpatient hospitalisation or prolongation of existing hospitalisation results in persistent or significant disability/incapacity consists of a congenital anomaly or birth defect
	Other 'important medical events' may also be considered serious if they jeopardise the participant or require an intervention to prevent one of the above consequences.
	NOTE: The term "life-threatening" in the definition of "serious" refers to an event in which the participant was at risk of death at the time of the event; it does not refer to an event which hypothetically might have caused death if it were more severe.
Serious Adverse Reaction (SAR)	An adverse event that is both serious and, in the opinion of the reporting Investigator, believed with reasonable probability to be due to one of the trial treatments, based on the information provided.
Suspected Unexpected Serious Adverse Reaction (SUSAR)	A serious adverse reaction, the nature and severity of which is not consistent with the information about the medicinal product in question set out in the reference safety information: • in the case of a product with a marketing authorisation, this could be in the summary of product characteristics (SmPC) for that product, so long as it is being used within its licence. If it is being used off label an assessment of the SmPC's suitability will need to be undertaken.

Version 5.0 22 July 2021 Page 53 of 82

in the case of any other investigational medicinal product, in the
investigator's brochure (IB) relating to the trial in question.

NB: "Severe" is often used to describe intensity of a specific event, which may be of relatively minor medical significance. "Seriousness" is the regulatory definition as supplied above.

10.2 Operational reporting for (S)AEs

Adverse events (AEs) will be recorded, notified, assessed, reported, analysed and managed in accordance with the Medicines for Human Use (Clinical Trials) Regulations 2004 (as amended) and this protocol. All AEs occurring during the trial that are observed by the Investigator or reported by the participant will be recorded in the participant's medical records whether or not attributed to trial medication.

All adverse reactions must be recorded within the eCRF.

All Serious Adverse Events (SAEs) occurring during the trial must be recorded in the eCRF.

The following are not considered be to be SAEs for the purposes of this trial.

- Routine treatment or monitoring of heart failure not associated with deterioration in heart failure.
- Treatment which was elective or pre-planned, for a pre-existing non-cardiac condition not associated with any deterioration in heart failure, e.g. pre-planned hip replacement operation which does not lead to further complications.
- Treatment on an emergency, outpatient basis for an event not fulfilling any of the definitions of serious as given above and not resulting in hospital admission.
- Admissions for social reasons not associated with a deterioration of heart failure.

All SAEs will be reported to the IDMC and analysed as part of the final trial results.

Full details of SAEs will be recorded in the electronic Case Report Form. The following information will be collected:

- full details in medical terms and a case description
- event duration (start and end dates, if applicable)
- action taken
- outcome
- · seriousness criteria
- causality (i.e. relatedness to trial drug / investigation), in the opinion of the investigator
- if related, whether the reaction would be considered expected or unexpected.

Any change of condition or other follow-up information should be added to the eCRF as soon as it is available or at least within 24 hours of the information becoming available. Events will be followed up until the event has resolved or a final outcome has been reached.

Assessment of Adverse Events

All adverse events must be assessed for seriousness. All SAEs must also be assessed for severity, causality and expectedness with reference to this protocol and the Reference Safety Information (RSI).

Version 5.0 22 July 2021 Page 54 of 82

Assessment of seriousness

An adverse event will be considered serious if it:

- results in death
- is life threatening
- requires hospitalisation or prolongation of existing hospitalisation
- results in persistent or significant disability or incapacity
- consists of a congenital anomaly or birth defect
- requires intervention to prevent one of the above
- Is an event of special interest as defined above

Assessment of causality

i.e. Does the event have a "reasonable causal relationship" with the trial IMPs? The following categories are used:

- **Yes** the causal and temporal relationship between the event and the absence of a more likely explanation suggest that the trial IMP is the most likely cause.
- No the event is not considered related to the trial IMPs.

Causality will be assigned for each IMP the participant is randomised to receive.

Should an SAE be considered unrelated to the administration of either trial drug then the causality of the event will be collected taking into consideration other factors, for example, concomitant medications or co-morbidities, etc.

Assessment of causality is the responsibility of the Principal Investigator or medically-qualified designee(s) at each site. The CI, their delegate(s), or the Sponsor may provide an opinion regarding causality but cannot downgrade the PI's assessment.

Assessment of expectedness

Should the event be considered to be related to the trial IMP(s), an assessment should be made regarding the expectedness of the reaction i.e. whether the reaction is a recognised adverse effect of the IMP(s).

Expected - consistent with the relevant product information documented in the RSI(s). **Unexpected** - not consistent with the relevant product information documented in the RSI(s).

The CI, their delegate(s) or the Sponsor have overall responsibility for assigning expectedness as per the RSI(s) and providing the final assessment of the event. The reporting investigator may provide an opinion on the expectedness of an event and this will be taken into account.

Assessment of severity

This should be assessed and described using the following categories:

- Mild awareness of event but easily tolerated
- Moderate discomfort enough to cause some interference with usual activity
- Severe inability to carry out usual activity.

Recording and reporting of SAEs

All reportable SAEs (see section 9.3) arising during the clinical trial will be recorded in the eCRF as soon as reasonably practicable and in any event within 24 hours of first becoming aware of the event. Any follow-up information should also be reported.

Version 5.0 22 July 2021 Page 55 of 82

- If recording via the eCRF is not possible, a paper SAE form should be completed. The SAE form is downloaded from www.glasgowctu.org, printed, completed and signed. A paper copy of the SAE form is filed in the Investigator Site File at each site should this website be unavailable. The completed form is faxed to the Glasgow Clinical Trials Unit Pharmacovigilance (PV) Office on [name]. If fax is not possible, a copy of the SAE form should be scanned and emailed to [contact].
- If necessary a verbal report can be provided by contacting the PV Office on [name]. This must be followed up as soon as possible with an electronic or written report.

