10.3 Serious Adverse Events (Sponsor reportable events)

Patiromer, spironolactone and eplerenone have well-understood safety profiles. Previous clinical trials have shown the combination of drugs to be well-tolerated (12). However, when the IMPs are used in combination there remain potential concerns regarding the effects of the IMP(s) on serum potassium.

In addition, participants in this trial are expected to have high rates of hospitalisations, cardiovascular events and death due to cardiac disease and related co-morbidities that are unlikely to be attributable to treatment with the trial IMP(s). These events will, however, inform the primary and secondary endpoints of the trial and will be subject to monitoring by the Data Monitoring Committee. As such these event will be recorded within the eCRF as per section 9.2.

Where the medicines are used in combination, the principle concern is changes in serum potassium and/or magnesium. For the purposes of pharmacovigilance, safety reporting will focus on the occurrence of hypokalaemia, hyperkalaemia, hypomagnesaemia, and events associated with these conditions, in particular potentially harmful renal insufficiencies.

Monitoring of non-reportable events

Non-reportable events will be monitored during the study. If deemed necessary, an initially non-reportable event may be added to the list of events reported to Sponsor. The process for this will be documented separately.

The following will be recorded on the eCRF as Serious Adverse Events and will be subject to expedited reporting to the sponsor:

- Any SAE that is considered, in the Investigator's opinion, related to the administration of any of the IMPs used in the trial, whether individually or in combination.
- Any incidence of an acute kidney injury meeting the criteria of a serious adverse event.
- Renal failure associated with a requirement for renal dialysis/ultrafiltration; and deaths associated with renal failure as evidenced by a preceding eGFR of 10ml/min/L/1.73m²
- SAEs associated with one of the following electrolyte disturbances
 - Severe hypokalaemia defined as serum potassium <3.0mmol/L
 - Severe hyperkalaemia defined as a serum potassium> 6.5mmol/L
 - Severe hypomagnesaemia defined by a serum magnesium <0.5mmol/L

Suspected Unexpected Serious Adverse Reactions (SUSARs)

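### The causality scale in Protocol section 10.2 is stricter than the adverse-reaction definition in 10.1, so some serious events can miss SAR or SUSAR classification

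*Protocol*

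**What the plan says.** Three wordings of the causal test stand in the current protocol.

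- **Adverse reaction (section 10.1).** The link "is at least a reasonable possibility, i.e. the relationship cannot be ruled out". The same entry lets more than one party make the judgement: "All cases judged by either the reporting medically qualified professional or the Sponsor as having a reasonable suspected causal relationship" to the trial medication qualify.
- **Serious adverse reaction (section 10.1).** A serious event that the reporting investigator "believed with reasonable probability to be due to one of the trial treatments".
- **Causality assessment (section 10.2).** The section first asks whether there is a reasonable causal relationship, then offers two categories. *Yes* rests on timing and "the absence of a more likely explanation", which together "suggest that the trial IMP is the most likely cause". *No* means that "the event is not considered related to the trial IMPs". There is no intermediate category.

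The answer is used further on. Section 10.2 asks for expectedness only when an event is considered related. Section 10.3 expedites to the sponsor any SAE that the investigator considers "related to the administration of any of the IMPs used in the trial". It makes a SUSAR depend on the PI or a delegate having assessed the SAE as related.

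**The concern.** A definition and the scale used to apply it should set the same threshold. Here the definition asks whether a link can be excluded, while the scale asks whether the IMP is the leading explanation. Section 10.3 expects high rates of hospitalisation, cardiovascular events and death from cardiac disease and co-morbidity, so another plausible cause will often be available. A site that follows 10.2 literally would answer *No* for some events that 10.1 calls reactions. At stake are the SAR and SUSAR labels and, for some events, expedited reporting to the sponsor, the MHRA and the REC.

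**Working it through.** The plan states no figure on this point and no arithmetic applies. The check sets the passages side by side and follows one event through them.

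1. **Order the thresholds.** If the IMP is the leading explanation, a link plainly cannot be excluded. The converse fails: a link may be impossible to exclude while something else is likelier. Events meeting *Yes* in 10.2 are therefore a strict subset of events meeting the adverse-reaction definition in 10.1. The SAR wording is a separate expression, and the protocol does not tie it to either of the other two.

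2. **Take an event in the gap.** Suppose an SAE that an IMP may reasonably have caused, with progression of heart failure the likelier cause. It meets the 10.1 adverse-reaction definition. It fails *Yes*, because a more likely explanation exists. The only remaining answer is *No*.

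3. **Follow that *No* through the protocol.**

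| Step | Rule | Effect of *No* |
|---|---|---|
| eCRF recording (10.2) | All SAEs are recorded | None |
| Expectedness (10.2) | Assessed only if related | Not assessed |
| SAR status (10.1) | Reporting investigator's opinion | Can be missed |
| Expedited to sponsor (10.3), first criterion | Investigator considers it related | Not met |
| Expedited to sponsor (10.3), other criteria | Serious acute kidney injury; renal failure with dialysis or ultrafiltration, or related death; SAE with potassium <3.0 or >6.5 mmol/L, or magnesium <0.5 mmol/L | None: no test of relatedness |
| SUSAR status (10.3) | PI or delegate assessed it as related, and it is unexpected | Can be missed |
| IDMC review (10.2, 11.5) | All SAEs are reported; data reviewed unblinded | None |
| Final tabulation (11.3) | By system organ class and preferred term | None |

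4. **Direction.** Because one set lies inside the other, the mismatch can only move events from related to unrelated.

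5. **Non-serious events.** Section 10.2 requires a causality assessment for SAEs only. It also requires all adverse reactions to be entered in the eCRF, and SAP section 2.7 lists the non-serious ones. Neither document says which threshold selects them. If sites use the 10.1 definition directly, nothing is lost. If they use the 10.2 scale, the same gap applies. The documents do not settle this.

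6. **Size.** The documents contain no count or rate of events with a possible but not leading link to an IMP, so the number misclassified cannot be estimated.

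**The case against.** The case on the other side is substantial, and much of it stands.

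- **The gap may be narrower than the words suggest.** The 10.1 entry itself tells the assessor to consider a valid alternative cause, and 10.2 opens with the milder question about a reasonable relationship. This is fair, but weighing an alternative is not the same as requiring that none be likelier. The text of the *Yes* category remains the operative instruction.
- **Others can correct the site.** Under 10.1 the Sponsor may judge an event a reaction. Under 10.4 the CI confirms the causality of all SAEs. Section 10.2 forbids only downgrading of the PI's view. These are real but partial safeguards: the SUSAR rule in 10.3 names the assessment of the PI or delegate alone, and no other threshold is given to the CI.
- **The main expected harms are protected.** The causality-independent list in 10.3 covers the renal and electrolyte events that the protocol names as its principal concern. This stands. Other serious reactions, symptomatic hypotension for example, are outside the list.
- **The sponsor may hear of every SAE anyway.** The PI duties in 10.4 read as though all SAEs go to the Sponsor within 24 hours. If that is what happens, the loss is confined to SAR and SUSAR labels and onward reporting. Section 10.3 is narrower, so this cannot be relied on.
- **The trial closed early.** SAP section 1.6.1 gives 4 randomised participants, 1.6.3 rules out formal analysis, and 2.7 lists all their SAEs whatever the causality. The practical effect on the final report is small.

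**Conclusion.** The inconsistency is in the current text and nothing elsewhere resolves it. It concerns the classification of SAEs as SARs or SUSARs, and expedited reporting outside the causality-independent list in 10.3. Its direction is certain if sites apply 10.2 as written; its size is unknown. It should be corrected because the correction is cheap, not because a large loss has been shown.

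Three stronger readings are tempting, and the documents do not support them.

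- **A reader might infer that most possible reactions are lost.** Frequent competing causes make the gap relevant, but no figure says how many events fall into it.
- **A reader might infer that the safety record as a whole leans towards no harm.** All SAEs are recorded, go to the IDMC and are tabulated without regard to relatedness. The comparison of SAEs between arms does not use this answer.
- **A reader might try to size the gap with an attributable fraction.** Section 3 gives worsening renal function in RALES as 17% against 7%. The ratio is 17/7 = 2.43 and the fraction (2.43 − 1)/2.43 = 0.59, which might suggest that 41% of such events are miscoded. That does not follow. The 41% (7/17) is the share expected without the drug, not drug effects coded *No*. If the test were a share above one half, at 59% every such event would pass it. A group fraction is not a judgement on one patient, and the likeliest of several causes need not exceed one half. Section 4.8 also makes a fall in eGFR of more than 30% a safety endpoint, and 10.3 expedites serious acute kidney injury regardless.

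**What to change.** In section 10.2, replace the *Yes* text with the 10.1 threshold, that a causal link is "at least a reasonable possibility, i.e. the relationship cannot be ruled out", and reserve *No* for events with no reasonable possibility of a link. Align the SAR definition in 10.1 to the same threshold; changing 10.2 alone would still leave two wordings. State whether the same test selects the non-serious adverse reactions for the eCRF.

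The cost is a short wording change in the protocol and the matching eCRF guidance. The downside is that somewhat more events will be reported as related. Given the early closure, a note in SAP section 2.7 stating which threshold lay behind the listed reactions would serve readers of the final report at almost no cost.

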10.3 Serious Adverse Events (Sponsor reportable events)

Patiromer, spironolactone and eplerenone have well-understood safety profiles. Previous clinical trials have shown the combination of drugs to be well-tolerated (12). However, when the IMPs are used in combination there remain potential concerns regarding the effects of the IMP(s) on serum potassium.

In addition, participants in this trial are expected to have high rates of hospitalisations, cardiovascular events and death due to cardiac disease and related co-morbidities that are unlikely to be attributable to treatment with the trial IMP(s). These events will, however, inform the primary and secondary endpoints of the trial and will be subject to monitoring by the Data Monitoring Committee. As such these event will be recorded within the eCRF as per section 9.2.

Where the medicines are used in combination, the principle concern is changes in serum potassium and/or magnesium. For the purposes of pharmacovigilance, safety reporting will focus on the occurrence of hypokalaemia, hyperkalaemia, hypomagnesaemia, and events associated with these conditions, in particular potentially harmful renal insufficiencies.

Monitoring of non-reportable events

Non-reportable events will be monitored during the study. If deemed necessary, an initially non-reportable event may be added to the list of events reported to Sponsor. The process for this will be documented separately.

The following will be recorded on the eCRF as Serious Adverse Events and will be subject to expedited reporting to the sponsor:

- Any SAE that is considered, in the Investigator's opinion, related to the administration of any of the IMPs used in the trial, whether individually or in combination.
- Any incidence of an acute kidney injury meeting the criteria of a serious adverse event.
- Renal failure associated with a requirement for renal dialysis/ultrafiltration; and deaths associated with renal failure as evidenced by a preceding eGFR of 10ml/min/L/1.73m²
- SAEs associated with one of the following electrolyte disturbances
 - Severe hypokalaemia defined as serum potassium <3.0mmol/L
 - Severe hyperkalaemia defined as a serum potassium> 6.5mmol/L
 - Severe hypomagnesaemia defined by a serum magnesium <0.5mmol/L

Suspected Unexpected Serious Adverse Reactions (SUSARs)

Any SAE assessed as related to trial IMP(s) by the PI or delegate, and unexpected (not documented as an expected reaction to the IMP(s) within the RSI(s)) by the CI, their delegate, or the Sponsor will be classified as a SUSAR and subject to expedited reporting to the Medicines and Healthcare products Regulatory Agency (MHRA) and the Research Ethics Committee (REC). Should the CI disagree with the PI's assessment of causality, both opinions will be provided on the report.

Version 5.0 22 July 2021 Page 56 of 82

The Sponsor will inform the MHRA and the REC of SUSARs within the required expedited reporting timescales:

- Fatal or life threatening SUSARs not later than 7 days of Sponsor awareness that the case fulfils the criteria for a fatal or life threatening SUSAR, and any follow up information within a further 8 days.
- All other SUSARs not later than 15 days of Sponsor awareness that the case fulfils the criteria for a SUSAR.

The Sponsor will report SUSARs to the MHRA via the MHRA eSUSAR reporting system and to REC by email with accompanying CTIMP Safety Report Form.

